2. STATISTICAL HYPOTHESES

All objectives in this SAP are exploratory.

3. SAMPLE SIZE DETERMINATION

As described in the Section 1.2.2, the sample sizes in the various phases of the study are determined by the treatment pathways starting with the core study.

POPULATIONS (ANALYSIS SETS) FOR ANALYSIS 4.

Table 1: **Description of Analysis Sets**

Analysis Sets	Description
All Randomized Set (RND)	The randomized analysis set includes all participants who were randomized in the core study.
Ponesimod Analysis Set (PAS)	This set includes all subjects who received at least one dose of ponesimod at any time during the core and/or the extension study.
Echocardiography Analysis Set (ECHO)	This includes all subjects in the PAS who have at least one echocardiography assessment after first dose of ponesimod.
Optical Coherence Tomography Analysis Set (OCT)	This includes all subjects in the PAS who have at least one OCT assessment after first dose of ponesimod.

An overview of the different analysis sets and their usage is given in Table 2 below.

Usage of Analysis Sets Table 2:

Analyses/Data Displays	RND	PAS	ECHO	OCT
Disposition	✓	✓		
Demographic characteristics		~		
Baseline characteristics		~		
Medical history		~		
Previous and concomitant medications		 ✓ 		
Protocol deviations		√*		
Treatment exposure		~		
Efficacy: Relapse		~		
Efficacy: MRI		~		
Efficacy: Neurological		~		
Efficacy: Ophthalmological				 ✓
Safety: Holter ECG		✓		

Safety: Echocardiography		\checkmark	
Safety: All other endpoints	~		
All subject listings	~		

*Subset on subjects entering the extension study.

ECG = electrocardiogram; ECHO = Echocardiography analysis set; OCT = Optical coherence tomography analysis set; PAS = Ponesimod analysis set; RND = All-randomized analysis set.

5. STATISTICAL ANALYSES

5.1. General Considerations

5.1.1. Dates, times and days

Core study treatment start date: date of first administration of study drug (ponesimod or placebo) in AC-058B201.

Extension study treatment start date: date of first administration of ponesimod in AC-058B202.

Ponesimod start date (PSD): date of first administration of ponesimod:

- for subjects randomized to ponesimod in the core study, this is the date of the first study drug administration in the core study.
- for subjects randomized to placebo in the core study and enter the extension, this is the date of the first study drug administration in the extension study.

Ponesimod EOT / ponesimod end date: defined as the latest study treatment end date as recorded on the Study Drug Log (ECENDTC in SDTM.EC where ECCAT = 'STUDY DRUG LOG').

Extension End-of-Treatment (eEOT) / **extension study treatment end date:** equal to the Ponesimod EOT / Ponesimod end date as defined above for subjects entering the extension study. Missing for subjects not entering the extension study.

Core End-of-Study (cEOS) date: the EOS date in the core study, defined as DSSTDTC in SDTM201.DS, where DSSCAT='STUDY TERMINATION'. If the subject died, then EOS date is set to death date, where death date is defined as SDTM201.DD.DDDTC.

Extension End-of-Study (eEOS) date: the EOS date in the extension study, defined as DSSTDTC in SDTM202.DS, where DSSCAT='STUDY TERMINATION'. If the subject died, then EOS date is set to death date, where death date is defined as SDTM202.DD.DDDTC. Missing for subjects not entering the extension study.

Last study date: defined as core EOS date for subjects who did not enter the extension study, and Extension EOS date for subjects who did enter the extension study.

Ponesimod Study Day: defined as the number of days elapsed since ponesimod start date (PSD) plus 1 (e.g., Ponesimod Study Day 1 is the day of first administration of ponesimod). For dates prior to ponesimod start date (PSD), study day is the negative number of days elapsed between the date under consideration and the day of first administration of ponesimod. Therefore, the ponesimod study day is always different from 0.

5.1.2. Baseline and change from baseline

The ponesimod baseline is defined as the last non-missing assessment performed prior to the first administration of ponesimod in either the core study (for subjects randomized to ponesimod in AC-058B201) or the extension study (for subjects randomized to placebo in AC-058B201 and proceeding to the extension study).

Assessments that were taken on the date of the first intake of ponesimod will prioritize scheduled visit assessments over unscheduled visit assessments, unless the time is available and it indicates the unscheduled visit assessment was performed later than the scheduled assessment, but prior to the first administration of ponesimod.

5.1.3. Planned Pregnancy Interruptions

Planned pregnancy interruptions will be excluded for definition of exposure, treatment-emergent adverse events and other safety variables including AEs, laboratory tests, pulmonary function tests (PFTs), vital signs and ECGs.

Planned pregnancy interruptions will not be excluded for efficacy analyses or for study duration.

Interruptions for planned pregnancies are identified in the database as defined in Section 5.2.1.5. Determination of the period of planned pregnancy interruption is described in Section 5.1.4.

5.1.4. Treatment-emergent definition

For the purpose of safety evaluations, the treatment-emergent period is defined as the time from first administration of ponesimod up to 15 days (inclusive) after last administration of ponesimod as study drug.

Assessments on the date of first intake of ponesimod are considered treatment-emergent, unless they are clearly documented to be prior to first intake of ponesimod.

Note that, as per Section 5.1.3, planned pregnancy interruption period is excluded from treatmentemergent definition and other related variables.

The period of planned pregnancy interruption will be excluded from the treatment-emergent period for subjects with planned pregnancy interruption and restart of the treatment prior to the EOS date. Therefore, the treatment-emergent period for these subjects will consist of periods: 1. From the first dose on the ponesimod start date up to the last dose prior to the pregnancy interruption +15 days, and

2. From the first dose of study drug after the pregnancy interruption up to EOT+ 15 days.

In order to assess events that occur during the pregnancy interruption, a new "pregnancy interruption emergent period" is defined as from the last dose prior to pregnancy interruption + 16 days to the minimum of (first dose after pregnancy interruption - 1 day, EOS date).

Treatment-emergent definitions are applicable to all safety variables, e.g., AEs, laboratory tests, pulmonary function tests (PFTs), vital signs and ECGs.

CONFIDENTIAL – FOIA Exemptions Apply in U.S. Status: Approved, Date: 20 September 2023

5.1.5. Last on-treatment definition

Last on-treatment value/assessment is defined for all subjects at the last value observed for the subject up to the ponesimod EOT date + 1 day.

5.1.6. Post-treatment-emergent definition

The post-treatment-emergent period is defined as follows:

The start date of the period is the date of last administration of ponesimod as study drug plus 16 days (inclusive). See Section 5.1.4 for the definition of treatment-emergent, which is defined as the time from first administration of ponesimod up to 15 days (inclusive) after last administration of ponesimod as study drug.

The end date of the period is last study date [see Section 5.1.1].

5.1.7. Coding

The following coding dictionaries are used:

- Adverse events, Medical history, and ECHO findings are coded using MedDRA version 26.0
- Medications (previous and concomitant) are coded using the WHO-Drug Dictionary version March 2023 B3G
- ECG and Holter abnormalities are coded using ECG CDISC SDTM Controlled Terminology (Version 3.2 from 2017-09-29).

**** For ECG and Vital Signs (VS), Day 1 post-baseline assessments are also considered.

Except for last-on-treatment and last FU analysis visits, if more than one assessment falls in the same time window, the closest non-missing assessment to the target day will be taken (if equidistant then the earlier value is taken). Last-on-treatment and last FU analysis visits are always mapped to the last non-missing assessment within the window.

FU visits are derived separately from treatment-emergent visits and may result in additional records in the ADaM datasets (or flagging). Last on-treatment and FU visits are defined for AP3 only.

5.1.9. Analysis strategy for long-term safety and efficacy – analysis over the whole ponesimod period

To investigate the long-term safety and efficacy of ponesimod, analysis is performed over the combined core/TP1/TP2/TP3 periods (excluding the placebo period for subjects who received placebo in the core study). All data for all subjects who received at least one dose of ponesimod at any time are included. Analyses are performed by first randomized dose of ponesimod.

The following analysis periods are defined to support the objectives as defined in Section 1.1 and Analysis Strategy as defined above. This SAP focusses on AP3, however AP1 and AP2 are described here for historical continuity with previous analyses. See Figure 1 for an illustration of the treatment periods.

- Analysis Period 1 (AP1) (Core TP1): analyses over core and extension TP1 periods combined;
- Analysis Period 2 (AP2) (Core TP2): analyses over core, extension TP1 and TP2 periods combined;
- Analysis Period 3 (AP3) (Core TP3): analyses over all periods combined.

The placebo period is excluded from all analyses described in this SAP, however the placebo visits and events are kept in the pooled B201/B202 analysis data model (ADaM) datasets. All analyses are performed by first randomized dose of ponesimod, i.e., ponesimod 10 mg, ponesimod 20 mg and ponesimod 40 mg. Additional disposition tables are provided including the placebo arm in order to provide a complete overview of the transition of patients through the two studies as shown above.

Analysis Period	Start Date	End Date
AP1	Ponesimod start date	Minimum of [last study date, date of first administration of ponesimod in TP2 - 1 day]
AP2	Ponesimod start date	Minimum of [last study date, date of first administration of ponesimod in TP3 - 1 day]
AP3	Ponesimod start date	Last study date

Table 4:Analysis Periods

Analyses for Analysis Periods 1 and 2 were conducted for the Interim Analysis CSR and are not planned to be repeated for the Final CSR. For the Final CSR, only analyses for Analysis Period 3 will be performed.

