3.10.3.2 Pharmacodynamic analyses

- Absolute count and percent change in peripheral blood lymphocyte counts as a function of ponesimod dose and plasma concentrations at trough level (pre-dose) on Days 8 and 15 (Visits E2 and E3) and at Visits E4, E7, E9, E13 (EOT2), P2, P7, P14, P22, P30 and EOT3, as applicable.
- Post-treatment lymphocyte recovery 8, 30, and 90 days (at 90 days for patients performing TP2 and TP3, if applicable) after study drug discontinuation.
- Efficacy and safety parameters will be correlated with absolute lymphocyte counts and magnitude of reduction of lymphocyte counts on an exploratory basis.

Additional PK and PD relationships to efficacy and safety parameters may be investigated.

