1.2.2. AC-058B202 study design (extension study)

This was designed as a prospective, multicenter, multinational, randomized, double-blind, multiple-dose, uncontrolled, parallel group extension study in subjects with RRMS who completed their regular Week 24 (End-of-treatment [EOT]) Visit of the core study while still on study treatment. Investigators, contract research organizations (CROs), and subjects were blinded to previous study treatment assignments during the core and at the time of transition to the extension study. The Sponsor was blinded during the core study and has been unblinded to the core dose assignments during the extension study follow-up in order to perform the final analyses of the core study. The Sponsor was also unblinded to the extension study dose assignments.

The study was designed to investigate the long-term safety, tolerability, and efficacy of three doses of ponesimod.

This extension study comprises three treatment periods: treatment period 1 (TP1; up to 96 weeks), and treatment periods 2 and 3 (TP2 and TP3; up to 540 weeks combined).

Per the original design of the extension study, subjects who received treatment with ponesimod (10, 20, or 40 mg) during the core study continued their treatment on the same dose during TP1 of the extension study. Subjects who received placebo in the core study were re-randomized 1:1:1 to 10, 20, or 40 mg ponesimod at the start of TP1.

The Sponsor was unblinded to the core study treatment allocation following the database lock and final analysis of the core study. The results of these analyses showed that ponesimod at doses of 10 and 20 mg were well tolerated. The 40 mg dose was associated with an increased incidence of adverse events (AEs) of dyspnea, peripheral edema, cough and, possibly, infection-related AEs, while no significant efficacy benefit was achieved with this dose as compared to 20 mg. Consequently, the Sponsor decided to discontinue the 40 mg treatment arm and offer the subjects who were randomized to 40 mg to be re-randomized to either ponesimod 10 or 20 mg. This option was introduced as TP2 in protocol Amendment 2 (16 February 2012 [D-12.087]).

Subjects who completed at least Visit E9 (Week 48) of TP1 could be enrolled into TP2. In TP2, all subjects receiving 40 mg ponesimod in TP1 were re-randomized to 10 or 20 mg ponesimod in a 1:1 ratio. Subjects on 10 and 20 mg ponesimod continued with their previously allocated dose.

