At the Independent Data Monitoring Committee (IDMC) meeting on 29 June 2016, the committee requested Actelion to perform a formal evaluation of the benefit-risk profile of the 10 and 20 mg dose arms in the ongoing extension, with the aim to potentially switch all subjects receiving ponesimod 10 mg to the 20 mg dose. The Sponsor performed the analyses given the study was already unblinded and presented the results without interpretation to the IDMC for the committee members to evaluate. Following a review of this analysis, the IDMC recommended on 6 December 2016 that the 10 mg dose arm should be discontinued and that all subjects should be offered to

continue on 20 mg. This switch from ponesimod 10 mg to the 20 mg dose in TP3 was introduced in protocol Amendment 7 (29 March 2017 [D-17.152]). Subjects who received 10 mg ponesimod during TP2 were switched to 20 mg ponesimod in TP3 and subjects on 20 mg ponesimod in TP2 continued with the same dose in TP3.

The changes in the original study design over the course of the study have resulted in significant additional complexity (see Figure 1 for a summary) and many possible treatment pathways through the study. In addition, at the transitions between core and extension studies and between TP1 and TP2, some subjects were allowed treatment interruptions of up to 3 months according to the protocol.

AC-058B201 (Core Study)	AC-058B202 (Extension Study)				
24 weeks	Up to 96 weeks	Up to 540 weeks	Up to 90 days		
10 mg ponesimod –	10 mg ponesimod	→ 10 mg ponesimod → 20 mg ponesimod			
20 mg ponesimod –	20 mg ponesimod	→ 20 mg ponesimod → 20 mg ponesimod			
		▼ 10 mg ponesimod → 20 mg ponesimod			
40 mg ponesimod -	40 mg ponesimod	1:1 ▲ 20 mg ponesimod → 20 mg ponesimod			
	10 mg ponesimod	→ 10 mg ponesimod → 20 mg ponesimod			
Placebo –	►1:1:1	→ 20 mg ponesimod → 20 mg ponesimod			
	40 mg ponesimod	110 mg ponesimod \rightarrow 20 mg ponesimod			
		[™] 20 mg ponesimod → 20 mg ponesimod			
Transition	Exten	sion Treatment Periods			
Informed Consent	Period 1 Randomization	Period 2 Period 3	Follow-up*		
Up to Visit 11 3 days Week 24	Period 1 Visits: E1 until E13 (EC Period 1 Week: 1 until 96	DT2) Period 2 / 3 Visits: P1 until EOT3 Period 2 / 3 Week: 1 until 540			

Figure 1: Study design: Treatments and Periods

*Safety follow-up visits:

After treatment period 1: at 8 and 30 days after last dose of study drug After treatment period 2 and treatment period 3: at 8, 30 and 90 days after last dose of study drug

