Flags are derived according to project specific ranges for marked laboratory abnormalities as described in Section 6.7 (Appendix 8). Marked laboratory abnormalities are flagged to indicate the increasing severity of abnormally low ("LL", "LLL"), or high values ("HH", and "HHH") for each of the laboratory parameters listed.

In addition, the following abnormality flags are derived for ALT, AST, total bilirubin (TBIL), and alkaline phosphatase (ALP):

- ALT: ≥ 1 × upper limit of normal range (ULN), ≥ 3 × ULN, ≥ 5 × ULN, ≥ 8 × ULN, ≥ 10*ULN, ≥ 20*ULN;
- AST: $\geq 1 \times ULN$, $\geq 3 \times ULN$, $\geq 5 \times ULN$, $\geq 8 \times ULN$, $\geq 10 \times ULN$, $\geq 20 \times ULN$;
- ALT or AST: $\geq 3 \times ULN$, $\geq 5 \times ULN$, $\geq 8 \times ULN$, $\geq 10 \times ULN$, $\geq 20 \times ULN$;
- TBIL $\geq 2 \times ULN;$
- ALT or AST \ge 3 × ULN and TBIL \ge 2 × ULN (at the same sample date);
- ALT or AST \ge 3 × ULN and TBIL \ge 2 × ULN + AP < 2 × ULN (at the same sample date).

The following summaries will be produced for quantitative laboratory results by treatment group:

- Summary of absolute values for laboratory parameters: descriptive statistics by analysis visit (AP3 on the PAS);
- Summary of absolute values and absolute change from ponesimod baseline values for laboratory parameters: descriptive statistics by analysis visit (AP3 on the PAS);
- Summary of absolute values for ALT, AST, bilirubin and ALP: descriptive statistics by analysis visit (AP3on the PAS);
- Summary of absolute values for lymphocytes: descriptive statistics by analysis visit (AP3 on the PAS);
- Summary of absolute values and absolute change from ponesimod baseline values for ALT, AST, bilirubin and ALP: descriptive statistics by analysis visit (AP3 on the PAS);
- Summary of absolute values and absolute change from ponesimod baseline values for lymphocytes: descriptive statistics by analysis visit (AP3 on the PAS);
- Summary of percent change from ponesimod baseline values for lymphocytes: descriptive statistics by analysis visit (AP3 on the PAS);
- Summary of absolute values at ponesimod baseline, at last on-treatment and at each followup visit (FU7, FU30, FU90 and Last FU) for lymphocytes (completed/discontinued subjects with at least one follow-up value only): descriptive statistics (AP3 on the PAS); by Post-Treatment DMT subgroup ((Any DMT, including ponesimod), No DMT).

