5.5.2. Pharmacodynamics

The pharmacodynamic (PD) marker evaluated in this study is Total lymphocyte counts, which were measured as part of the clinical laboratory hematology tests.

The following parameters are collected:

- Absolute count in peripheral blood lymphocyte counts as a function of ponesimod dose and plasma concentrations at trough level (pre-dose) on Days 8 and 15 (Visits E2 and E3) and at Visits E4, E7, E9, E13 (EOT2), P2, P7, P14, P22, P30 and EOT3, as applicable.
- Post-treatment lymphocyte recovery 8, 30, and 90 days (only at 90 days for patients performing TP2 and TP3, if applicable) after study drug discontinuation.

The following summaries for peripheral blood lymphocyte counts as a function of ponesimod dose, as described in Section 5.4.5.1, will be produced:

- Summary of absolute values and absolute change from ponesimod baseline values for lymphocyte counts: descriptive statistics by analysis visit (AP3 on the PAS);
- Summary of percent change from ponesimod baseline values for lymphocyte counts: descriptive statistics by analysis visit (AP3 on the PAS);

In addition, the following plot, as described in Section 5.4.5.1 will be produced:

• Plot of percent change from ponesimod baseline values for lymphocyte counts: mean ± SE by analysis visit (AP3 on the PAS);

The following summaries for post-treatment lymphocyte count recovery, as described in Section 5.4.5.1, will be produced:

- Summary of absolute values at ponesimod baseline, at last on-treatment and at each followup visits (FU7, FU30, FU90 and Last FU)) for lymphocyte counts (completed/discontinued subjects with at least one follow-up value only): descriptive statistics (AP3 on the PAS); by Post-Treatment DMT subgroup ((Any DMT, including ponesimod), No DMT).
- Summary of percent change from ponesimod baseline to last on-treatment and to each follow-up visit (FU7, FU30, FU90 and Last FU)) for lymphocyte counts (completed/discontinued subjects with at least one follow-up value only): descriptive statistics (AP3 on the PAS); by Post-Treatment DMT subgroup ((Any DMT, including ponesimod), No DMT).

In addition, the following plots, as described in Section 5.4.5.1, will be produced:

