5.5.3. Pharmacokinetic/Pharmacodynamic Relationships

The following endpoint, "Efficacy and safety parameters will be correlated with absolute lymphocyte counts and magnitude of reduction of lymphocyte counts on an exploratory basis." was added to explore the objective: dose response relationship of 10, 20, and 40 mg ponesimod on lymphocyte count, magnetic resonance imaging (MRI) endpoints, annualized relapse rate (ARR), and safety endpoints.

Analyses to address dose decisions were presented in the Interim Analysis CSR and are not planned to be addressed in the Final CSR.

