6.2.1. Changes to the analyses planned in the study protocol

	are planned as part of this SAP.	protocol writing. Such an analysis
	Subjects are summarized by pooled	would not be interpretable.
	dose groups (based on first	-
	randomized dose of ponesimod)	
	only.	
5.3	For ARR, it is stated that "In	"Number of documented relapses in
	addition, the treatment effect on	a fixed 24-month period cannot be
	aggregate ARR will be tested by	determined for ponesimod baseline
	means of negative binomial	(of placebo switchers) and so the
	regression adjusted by treatment,	value prior to start of the core is
	region, number of documented	used. The categories are modified
	relapses (≤ 2 and > 2) past 24	as only a very small proportion of
	months prior to screening, EDSS	subjects would fall into $a > 2$
	[Expanded Disability Status Scale]	category.
	at baseline (CRF Visit 2) and total	EDSS is categorized as the log-rank
	number of T1 Gd+ [gadolinium-	test (which is displayed alongside
	enhancing] lesions at baseline." This	the Cox regression results) can only
	is similarly applied for the Cox	take categorical variables as
	proportional-hazard regression	covariates. Given the small sample
	model for time to first relapse, and	size only the two more important
	negative binomial model for MRI	covariates are selected.
	endpoints.	The same two covariates are used
	Only two covariates will be included	for all adjusted analyses (i.e., also
	in the adjusted models: EDSS score	for the negative binomial model for
	category (≤ 3.5 and > 3.5) based on	ARR and MRI) for consistency.
	extension baseline, and relapses in	
	the 2 years prior to screening in the	
	core study (≤ 1 and ≥ 2).	
	EDSS is defined as a categorical	
	variable. Number of documented	
	relapses categorization is modified	
5.2	$\frac{1}{100} \le 2 \text{ and } \ge 2^{\circ} \text{ to } \le 1 \text{ and } \ge 2^{\circ}.$	T1
5.5	It is stated that "Different methods	I ne interim analysis covers a period
	data and to nonform consistivity	of almost 9 years and higher drop-
	and to perform sensitivity	long pariod Imputation of missing
	a result of missing information. The	data over this long of a period would
	methods will include an analysis	be difficult to interpret
	which treats missing values as a	be difficult to interpret.
	success and an analysis which treats	
	missing values as a failure "	
	These sensitivity analyses are not	
	planned in this SAP for some of the	
	endpoints.	

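### SAP 5.5.2 presents lymphocyte counts by ponesimod dose using tables grouped by first randomized dose, and the protocol's exposure by dose has no subject-years summary and no entry in SAP 6.2

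*SAP*

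**What the plan says.** **Grouping.** SAP 5.1.9: "All analyses are performed by first randomized dose of ponesimod, i.e., ponesimod 10 mg, ponesimod 20 mg and ponesimod 40 mg". The SAP 6.2.1 row for protocol 5.3 repeats it: "Subjects are summarized by pooled" dose groups, based on first randomized dose, and in no other way.

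**Lymphocytes.** Protocol 3.10.3.2 asks for "peripheral blood lymphocyte counts as a function of ponesimod dose and plasma concentrations at trough level". SAP 5.5.2 keeps the first half: "The following summaries for peripheral blood lymphocyte counts as a function of ponesimod dose, as described in Section 5.4.5.1, will be produced". The tables it points to in SAP 5.4.5.1 are by treatment group, for example "Summary of percent change from ponesimod baseline values for lymphocytes: descriptive statistics by analysis visit (AP3 on the PAS".

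**Dose changes.** SAP 1.2.2: "In TP2, all subjects receiving 40 mg ponesimod in TP1 were re-randomized to 10 or 20 mg ponesimod in a 1:1 ratio"; and later, "This switch from ponesimod 10 mg to the 20 mg dose in TP3 was introduced in protocol Amendment 7 (29 March 2017".

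**What was openly dropped.** SAP 1.1 and 6.2.1 remove the dose-response objective and its modelling. SAP 5.5.3 does the same for the PK/PD correlations: "Analyses to address dose decisions were presented in the Interim Analysis CSR and are not planned to be addressed in the Final CSR".

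**Exposure.** Protocol 5.8 describes exposure in terms of both duration and dose, by treatment group. SAP Table 10 derives exposure for each treatment period, but the tables in SAP 5.4.2.1 cover AP3 duration, duration categories, interruptions and compliance, with no dose item. Period-level exposure goes to listings (5.4.2.1), as does actual treatment in each period (5.2.2). SAP 5.2.2 also plans a TP3 disposition table by treatment pathway, which counts subjects.

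**A stray sentence.** SAP 5.4 bases safety analyses on the intervention actually received, unless stated otherwise. Section 5.1.9 and Appendix 2 do state otherwise.

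**The concern.** Total lymphocyte count is the study's PD marker, and its by-dose summary survived when the rest of the dose-response work was cut. Followed as written, the Final CSR would show 10, 20 and 40 mg columns under text that calls them dose, while at later visits differences between columns would follow the switching rules. A reader could conclude that 40 mg suppresses lymphocytes less than 20 mg.

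For exposure, 20 mg is the dose that everyone ends on, and the protocol's long-term safety statement rests on subject-years in the 20 mg group. Time on 20 mg also accrues in the '10 mg' and '40 mg' columns. Without subject-years by dose, the summary tables cannot say how much 20 mg exposure the study holds.

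**Working it through.** **1. Last scheduled sample on 40 mg.** Inputs: core 24 weeks, TP1 up to 96 weeks, visit window 14 days (protocol schedule); analysis windows from SAP Table 3.

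- Three-day transition (protocol 3.1.1): 24×7 + 3 + 96×7 + 14 + 1 = Day 858.
- Gap of about 90 days between core and extension (SAP 1.2.2 allows up to 3 months): 24×7 + 90 + 96×7 + 14 + 1 = Day 945.
- Former placebo patients, counted from their first ponesimod dose: 96×7 + 14 + 1 = Day 687.

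The Week 144 window is Days 926–1093, and Week 168 opens on Day 1094. So Week 144 can hold a scheduled on-40 mg sample only after a long gap, and Week 168 onward cannot. The margin, 1094 − 945 = 149 days, leaves room for the core Week 24 visit window, which the documents do not give. Table 3 has 8 windows (Weeks 1–24) plus 28 (Weeks 48–696) = 36 after baseline; Weeks 168–696 are (696 − 168)/24 + 1 = 23 of them.

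**2. Share of the '40 mg' column spent on 40 mg, at maximum follow-up.** TP1 lasts 60 weeks (E9 at Week 48 plus 12) to 96 weeks; TP2 and TP3 together last up to 540. Two titration weeks are removed, because 40 mg starts on Day 15.

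| Starters | TP1 60 weeks | TP1 96 weeks |
|---|---|---|
| 40 mg in core | (24+60−2)/624 = 13.1% | (24+96−2)/660 = 17.9% |
| Placebo in core | (60−2)/600 = 9.7% | (96−2)/636 = 14.8% |

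The range is about 10–18%. It is higher for anyone who leaves before 540 weeks of TP2 and TP3. Apart from titration, it is all of the time for anyone who stops in core or TP1.

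**3. What the lymphocyte table would show.** Protocol 1.3.2.2 gives mean Week 24 reductions of 49.8%, 65.3% and 68.6% on 10, 20 and 40 mg. Assume these persist. The protocol supports this: steady state in 4–5 days (1.3.2.1), no tachyphylaxis, stable counts on treatment, and return to baseline within 1–2 weeks of stopping (1.3.2.2). TP2 visits are 12 weeks apart.

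- TP2 '40 mg' column, 1:1 split: 0.5×49.8 + 0.5×65.3 = 57.55%.
- With 40% of them on 10 mg: 0.4×49.8 + 0.6×65.3 = 59.1%. With 60%: 0.6×49.8 + 0.4×65.3 = 56.0%.
- '20 mg' column: 65.3%. The gap is 65.3 − 57.55 = 7.75 points in favour of 20 mg, where Week 24 had 40 mg ahead by 68.6 − 65.3 = 3.3 points.
- TP3: 65.3% in all three columns.

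**4. Exposure.** Protocol 5.8 names two dimensions and the SAP tables carry one. SAP 6.2.1 and 6.2.3 have no row for protocol 5.8; their exposure-related rows concern planned pregnancy and the total-exposure subgroup. The size of the gap cannot be fixed from the documents, which give neither TP3 length nor retention. An upper bound for the '10 mg' column takes TP3 as starting on the Amendment 7 date. With extension entry between 1 April 2010 and 30 June 2011 (planned Q2 to Q2), 364.9 to 299.9 weeks have passed. This leaves 636 − 364.9 = 271 to 636 − 299.9 = 336 weeks on 20 mg: from 271/660 = 41% to 336/636 = 53% of maximum treatment time.

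**The case against.** The strongest reply is that nothing here is hidden. First-dose grouping is declared, the dose-response objective is withdrawn by name, and the phrase in 5.5.2 may be no more than carried-over protocol wording. The interim report covered core plus TP1, where group and maintenance dose coincide. In the Final CSR, scheduled samples after titration through Week 48 precede any TP2 switch. All lymphocyte values are listed, and so is actual treatment by period. All of this stands. It does not reach the retained summary, which SAP 6.2.3 presents as the output addressing the PD marker.

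On exposure, protocol 5.8 explicitly requires tabulation only of exposure time, and it does not ask in terms for subject-years by dose. That stands in part, which is why a declared departure is an acceptable remedy. It is also true that the '20 mg' column is clean after titration: those patients stay on 20 mg to the end. Leaving out 20 mg time held elsewhere understates the total but does not distort that group.

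SAP 5.5.1 does plan trough concentrations by treatment period and by dose, then describes the same summaries as by treatment group. That is PK, and it gives no rule for lymphocytes.

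Three stronger readings are tempting and not supported:

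- A reader might infer that no sample from Week 144 on can be on 40 mg. SAP 1.2.2 allows a core-to-extension gap of up to 3 months, and that can put one inside the Week 144 window.
- A reader might infer that dose by period appears only in listings. SAP 5.2.2 plans a TP3 disposition table by pathway, although it counts subjects, not time.
- A reader might infer that the first-dose safety tables are invalid. They are a legitimate summary by initial assignment.

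**Conclusion.** The point holds as a mismatch between two retained outputs and the grouping that supplies them. The window count (at least 23 of 36) follows from the schedule and Table 3. It counts defined windows, not samples, and the late windows will be sparse. The 10–18% share is a maximum-follow-up figure, not an estimate of observed exposure. The 57.6% against 65.3% rests on persistence of the Week 24 reductions and a 1:1 split. The exposure gap is certain as a matter of text: no subject-years by dose and no declaration. Its size in subject-years is unknown. All analyses are exploratory, so what is affected is how these two outputs are read. Severity is at the low end of should-fix.

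**What to change.** 1. In SAP 5.5.2, add a descriptive lymphocyte summary by dose taken on the sample date (study drug log), within treatment period. Label it partly non-randomized and confounded with time on study. Head the retained tables 'first randomized to X mg' and stop describing them as a function of dose.
2. In SAP 5.4.2.1, add subject-years by dose actually taken, within each first-dose group and in total; or declare the departure from protocol 5.8 in SAP 6.2.
3. As minor wording, align the sentence in SAP 5.4 on intervention received with 5.1.9 and Appendix 2.

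The cost is some SAP wording, one lymphocyte summary and one exposure table, built from the existing study drug log and the Table 10 period variables. No new data are needed, and the first-dose adverse event tables stay as they are.
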